9.3.3. Pharmacokinetic Analysis

Noncompartmental analysis will be conducted, and PK parameters such as maximum observed drug concentration, time to maximum observed drug concentration, area under the concentration versus time curve from time zero to infinity, and area under the concentration versus time curve from time zero to t, where t is the last time point with a measurable concentration will be reported for lebrikizumab. Other noncompartmental parameters such as apparent clearance, apparent volume of distribution, and half-life may be reported, as appropriate.

Exploratory graphical analyses relating lebrikizumab serum exposure and immunogenicity may be conducted.

9.3.4. Immunogenicity Analysis

The frequency and percentage of participants with pre-existing ADA and with TE ADA to lebrikizumab may be tabulated by treatment. TE ADA are defined as those with a titer 2-fold, 1 dilution, greater than the minimum required dilution if no ADA were detected at baseline, treatment-induced ADA, or those with a 4-fold, 2 dilutions, increase in titer compared to baseline if ADA were detected at baseline, treatment-boosted ADA.

The frequency of neutralizing antibodies and distribution of maximum titers may also be tabulated in TE ADA+ participants by treatment.

The relationship between the presence of antibodies to lebrikizumab and safety may be assessed.

9.4. Interim Analysis

No interim analyses are planned for this study. If an unplanned interim analysis is deemed necessary for reasons other than a safety concern, the protocol must be amended.

Unblinding details are specified in the unblinding plan section of the SAP or in a separate unblinding plan document.

9.5. Sample Size Determination

Approximately 24 participants will be enrolled in 2 dosing cohorts for at least 20 evaluable participants to complete the study. The sample sizes described are customary for Phase 1 studies evaluating safety and PK parameters and are not powered on the basis of statistical hypothesis testing. Each cohort will comprise approximately 12 participants with a randomization ratio of 5:1 between lebrikizumab and placebo. Participants who discontinue the study before completing may be replaced at the discretion of the sponsor and investigator. The replacement participant can complete the entire study period.

10. Supporting Documentation and Operational Considerations

10.1. Appendix 1: Regulatory, Ethical, and Study Oversight Considerations

10.1.1. Regulatory and Ethical Considerations

This study will be conducted in accordance with the protocol and with the following:

Consensus ethical principles derived from international guidelines including the Declaration of Helsinki and CIOMS International Ethical Guidelines

Applicable ICH GCP Guidelines, and

Applicable laws and regulations.

The protocol, protocol amendments, ICF, IB, and other relevant documents, for example, advertisements, must be submitted to an IRB/IEC by the investigator and reviewed and approved by the IRB/IEC before the study is initiated.

Any amendments to the protocol will require IRB/IEC approval before implementation of changes made to the study design, except for changes necessary to eliminate an immediate hazard to study participants.

Protocols and any substantial amendments to the protocol will require health authority approval prior to initiation except for changes necessary to eliminate an immediate hazard to study participants.

The investigator will be responsible for the following:

providing written summaries of the status of the study to the IRB/IEC annually or more frequently in accordance with the requirements, policies, and procedures established by the IRB/IEC

notifying the IRB/IEC of SAEs or other significant safety findings as required by IRB/IEC procedures

providing oversight of study conduct for participants under their responsibility and adherence to requirements of 21 CFR, ICH guidelines, the IRB/IEC, European regulation 536/2014 for clinical studies, if applicable, and all other applicable local regulations, and

reporting to the sponsor or designee significant issues related to participant safety, participant rights, or data integrity.

10.1.3 Informed Consent Process

Potential participants must be informed that their participation is voluntary. Participants will be required to sign a statement of informed consent that meets the requirements of 21 CFR 50, local regulations, ICH guidelines, privacy, and data protection requirements, where applicable, and the IRB/IEC or study center.

The medical record must include a statement that written informed consent was obtained before the participant was entered in the study and the date the written consent was obtained. The authorized person obtaining the informed consent must also sign the ICF.

Revised consents must be appropriately obtained using the correct approved ICFs for applicable study participants in accordance with sponsor and IRB/IEC consenting guidance.

A copy of the ICF must be provided to the participant and is kept on file.

10.1.3. Data Protection

Participants will be assigned a unique identifier by the sponsor (((((personal data. Any participant information, such as records, datasets or tissue samples, that are transferred to the sponsor will contain the identifier only. Participant names or any information which would make the participant identifiable will not be transferred.

The participant must be informed that () personal study-related data will be used by the sponsor in accordance with local data protection law. The level of disclosure must also be explained to the participant who will be required to give consent for their data to be used as described in the informed consent. This is done by the site personnel through the informed consent process.

The participant must be informed through the informed consent by the site personnel that their medical records may be examined by clinical quality assurance auditors or other authorized personnel appointed by the sponsor, by appropriate IRB/IEC members, and by inspectors from regulatory authorities.

The sponsor has processes in place to ensure information security, data integrity, and data protection. These processes address management of data transfer, and prevention and management of unauthorized access, disclosure, dissemination, alteration or loss of information or personal data. These processes include appropriate contingency plans for appropriate and timely response in the event of a data security breach.

The transfer of personal data is subject to appropriate safeguards through contractual agreements (such as the Standard Contractual Clauses) or other measures, including the General Data Protection Regulation.

10.1.4. Dissemination of Clinical Study Data

Communication of Suspended or Terminated Dosing

If a decision is taken to suspend or terminate dosing in the study due to safety findings, this decision will be communicated by Lilly to all investigators, for example, by phone or email, as soon as possible. It will be a requirement that investigators respond upon receipt to confirm that they understand the communication and have taken the appropriate action prior to further dosing any participants with study intervention. Any investigator not responding will be followed up by Lilly personnel prior to any further planned dosing. If a dose is planned imminently, Lilly

personnel will immediately, and continually, use all efforts to reach investigators until contact is made and instructions verified.

Reports

The sponsor will disclose a summary of study information, including tabular study results, on publicly available websites where required by local law or regulation.

The summary of results will be posted within the time frame specified by local law or regulation. If the study remains ongoing in some countries and a statistical analysis of an incomplete dataset would result in analyses lacking scientific rigor, for example, underpowered, or compromise the integrity of the overall analyses, for example, trial not yet unblinded, the summary of results will be submitted within 1 year after the end of the study globally or as soon as available, whichever is earlier.

Data

The sponsor does not proactively share data from Phase 1 clinical trials. Requests for access to Phase 1 clinical trial data are evaluated on a case by case basis taking into consideration the ability to anonymize the data and the nature of the data collected.

10.1.5. Data Quality Assurance

All participant data relating to the study will be recorded on printed or electronic CRFs unless transmitted to the sponsor or designee electronically, for example, laboratory data. The investigator is responsible for verifying that data entries are accurate and correct by physically or electronically signing the CRF.

The investigator must maintain accurate documentation, source data, that supports the information entered in the CRF. This includes laboratory tests, medical records, and clinical notes.

The investigator must review and confirm that data entries are accurate and complete throughout the duration of the study, by physically or electronically signing the CRF, as instructed by the sponsor. All completed CRFs must be signed prior to archival.

The investigator must permit study-related monitoring, audits, IRB/IEC review, and regulatory agency inspections and provide direct access to source documents.

Monitoring details describing strategy, for example, risk-based initiatives in operations and quality such as risk management and mitigation strategies and analytical risk-based monitoring, methods, responsibilities and requirements, including handling of noncompliance issues and monitoring techniques are provided in the Monitoring Plan.

The sponsor or designee is responsible for the data management of this study including quality checking of the data.

The sponsor assumes accountability for actions delegated to other individuals, for example, contract research organizations.

The sponsor or designee will perform monitoring to confirm that data transcribed into the CRF by authorized site personnel are accurate, complete, and verifiable from source documents; that the safety and rights of participants are being protected; and that the study is being conducted in

accordance with the currently approved protocol and any other study agreements, ICH GCP, and all applicable regulatory requirements.

Records and documents, including signed ICFs, pertaining to the conduct of this study must be retained by the investigator for the time period outlined in the clinical trial agreement unless local regulations or institutional policies require a longer retention period. No records may be destroyed during the retention period without the written approval of the sponsor. No records may be transferred to another location or party without written notification to the sponsor.

In addition, the sponsor or its representatives will periodically check a sample of the participant data recorded against source documents at the study site. The study may be audited by the sponsor or its representatives, or regulatory agencies at any time. Investigators will be given notice before an audit occurs.

Data Capture System

The investigator is responsible for ensuring the accuracy, completeness, legibility, and timeliness of the data reported to the sponsor.

An electronic data capture system will be used in this study for the collection of CRF data. The investigator maintains a separate source for the data entered by the investigator or designee into the sponsor-provided electronic data capture system. The investigator is responsible for the identification of any data to be considered source and for the confirmation that data reported are accurate and complete by signing the CRF.

Data collected via the sponsor-provided data capture system will be stored at a third-party. The investigator will have continuous access to the data during the study and until decommissioning of the data capture system. Prior to decommissioning, the investigator will receive or access an archival copy of pertinent data for retention.

Data from complaint forms submitted to the sponsor will be encoded and stored in the global product complaint management system.

10.1.6. Source Documents

Source documents provide evidence for the existence of the participant and substantiate the
((((E[∞] (((((E

Data that are reported on or entered in the CRF and are transcribed from source documents must be consistent with the source documents or the discrepancies must be explained. The investigator may need to request previous medical records or transfer records, depending on the study. Also, current medical records must be available.

Definition of what constitutes source data can be found in the site confirmation of source data.

10.1.7. Study and Site Start and Closure

First Act of Recruitment

The study start date is the date on which the clinical study will be open for recruitment of participants.

Study or Site Termination

The sponsor () designee reserves the right to close the study site or terminate the study at any time for any reason at the sole discretion of the sponsor. Study sites will be closed upon study completion. A study site is considered closed when all required documents and study supplies have been collected and a study-site closure visit has been performed.

The investigator may initiate study-site closure at any time, provided there is reasonable cause and sufficient notice is given in advance of the intended termination.

Reasons for the early closure of a study site by the sponsor or investigator may include but are not limited to

for study termination due to discontinuation of further study intervention development
for site termination due to

- failure of the investigator to comply with the protocol, the requirements of the IRB/IEC or local health authorities, the sponsor's procedures, or GCP guidelines
- inadequate recruitment, evaluated after a reasonable amount of time, of participants by the investigator, or
- total number of participants included earlier than expected.

If the study is prematurely terminated or suspended, the sponsor shall promptly inform the investigators, the IECs/IRBs, the regulatory authorities, and any contract research organization used in the study of the reason for termination or suspension, as specified by the applicable regulatory requirements. The investigator shall promptly inform the participant and should assure appropriate participant therapy and/or follow-up.

10.1.8. Publication Policy

r () () () () () () () ()
for publication by a peer-reviewed journal if the results are deemed to be of significant medical importance.

10.1.9. Sample Retention

Sample retention enables use of new technologies, response to regulatory questions, and investigation of variable response that may not be observed until later in the development of lebrikizumab or after lebrikizumab becomes commercially available.

Sample Type	Custodian	Retention Period After Last Participant Visit
Pharmacokinetic	Sponsor or designee	1 year
Immunogenicity	Sponsor or designee	Per local regulation or the IECs/IRBs requirements. Samples will be immediately destroyed once lebrikizumab is launched or there is no further request on testing the samples from China authority.
Hematology, chemistry, urinalysis, and hepatic monitoring (both central and local laboratory)	Sponsor or designee	These samples are destroyed after protocol-specific tests are performed, based on the requirements for the laboratory procedures, laws, regulations, or internal laboratory certification standard.

10.2. Appendix 2: Clinical Laboratory Tests

The tests detailed in the table below will be performed by the laboratories listed in Section 10.7.

In circumstances where the sponsor approves local laboratory testing in lieu of central laboratory testing, in the table below, the local laboratory must be qualified in accordance with applicable local regulations.

Protocol-specific requirements for inclusion or exclusion of participants are detailed in Section 5 of the protocol.

Additional tests may be performed at any time during the study as determined necessary by the investigator or required by local regulations.

Investigators must document their review of the laboratory safety results.

Laboratory or analyte results that could unblind the study will not be reported to investigative sites or other blinded personnel until the study has been unblinded.

I	I	Comments
Hematology		
Hematocrit	Cell morphology (RBC and WBC)	
Hemoglobin	Differential counts (% and absolute) of:	
Erythrocyte count (RBC)	Neutrophils	
Mean cell volume	Lymphocytes	
Mean cell hemoglobin	Monocytes	
Mean cell hemoglobin concentration	Eosinophils	
Leukocytes (WBC)	Basophils	
Platelets		
Clinical Chemistry		
Sodium	Total cholesterol	
Potassium	Total protein	
Chloride	Albumin	
Calcium	Total bilirubin	
Phosphorus	Direct bilirubin	
Glucose	Alkaline phosphatase	
Blood urea nitrogen or urea	Aspartate aminotransferase	
Creatinine	Alanine aminotransferase	
Uric acid	Gamma-glutamyl transferase	
Urinalysis		
Specific gravity	Urobilinogen	
pH	Blood	
Protein	Nitrite	
Glucose	Microscopic examination of sediment	
Ketones		
Bilirubin		
Other Tests		
Ethanol testing	Urine drug screen	Tests may be repeated locally at additional time points at the discretion of the investigator.
QuantiFERON®-TB Gold or T-SPOT®	Urine and serum pregnancy test (women of childbearing potential only)	
FSH (females only)		
Serology		
Hepatitis B surface antigen	HIV	
Hepatitis B core antibody	Hepatitis C antibody	

Pharmacokinetic Samples		Results will not be provided to the investigative sites.
Lebrikizumab concentration		
Immunogenicity (ADA) Samples		Results will not be provided to the investigative sites.
Anti-LY3650150 antibodies	Anti-LY3650150 antibodies neutralization	

Abbreviations: ADA = anti-drug antibody; FSH = follicle-stimulating hormone; HIV = human immunodeficiency virus; RBC = red blood cell; TB = tuberculosis; WBC = white blood cell.

10.2.1. Blood Sampling Summary

This table summarizes the approximate number of venipunctures and blood volumes for all blood sampling, screening, safety laboratories, and bioanalytical assays during the study.

Purpose	Blood Volume per Sample (mL)	Number of Blood Samples	Total Volume (mL)
Screening tests ^a	18.5	1	18.5
Hematology and chemistry ^a	5.5	11	60.5
Pharmacokinetics	3	13	39
Immunogenicity	10	5	50
Total			168
Total for clinical purposes			170

^a Additional samples may be drawn if needed for safety purposes.

10.2.2. Laboratory Samples to be Obtained at the Time of a Systemic Hypersensitivity Event

Purpose of collecting samples after a systemic hypersensitivity event

The samples listed in this appendix are not collected for acute study participant management. The sponsor will use the laboratory test results from these samples to characterize hypersensitivity events across the clinical development program.

When to collect samples after a systemic hypersensitivity event occurs

Collect the samples listed below if a systemic hypersensitivity event is suspected. The timing should be as designated in the table, assuming the participant has been stabilized.

Obtain follow-up predose samples at the next regularly scheduled laboratory sample collection, ideally prior to the next dose after the event, to assess post-event return-to-baseline values.

a All samples for hypersensitivity testing will be assayed by Lilly-designated laboratory. Results will not be provided to the study site. If samples are not collected or are collected outside the specified time period, this will not be considered a protocol deviation.

Abbreviations: ADA = anti-drug antibodies; IL = interleukin.

What information to record

Record the date and time when the samples are collected.

Allowed additional testing for participant management

The investigator may perform additional tests locally, if clinically indicated, for acute study participant management.

10.3. Appendix 3: Adverse Events and Serious Adverse Events: Definitions and Procedures for Recording, Evaluating, Follow-up, and Reporting

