1.3. Schedule of Activities (SoA)

	Screening	Inpatient Period				Follow-up Period										Comments			
		1	2	3	4	5	6	7	8	9	10	11	12	13	14	15			
Visit	1																		
Day	-28 to -2	-1	1	2	5	8	11	15	22	29	36	43	50	57	64	71	85	99	120
Procedure							± 1	± 2	± 3	± 3	± 3	± 3 or ED							
Informed consent	X																		
Medical history and demographics	X																		
Review and confirm inclusion/exclusion criteria	X	X																	
Admission to CRU		X																	
Discharge from CRU					X														
Outpatient visit	X					X	X	X	X	X	X	X	X	X	X	X	X		
Randomization			X														.		
Height	X																		
Weight and BMI	X	X															X		
Ultrasound examination		X															Ultrasound examination (for example, abdominal) as deemed clinically necessary.		
Serology	X																See Section 10.2		
TB testing	X																See Section 10.2		
Chest x-ray (posterior-anterior view)		X															A lateral chest x-ray may be performed if clinically or radiologically indicated.		

Ethanol test and urine drug screen	X	X															X	May be repeated at additional time points at (discretion.
FSH (females only)	X																	See Sections 10.2 and 10.4.
Pregnancy test (WOCBP only)	X	X															X	Serum test at screening only. Urine test at all other time points. See Sections 10.2 and 10.4.
Lebrikizumab or placebo administration			X															See Section 6.1.
Physical examination	X	X		X													X	Full physical examination at screening or Day -1. Symptom-directed examinations at other times, and at (discretion.
Vital signs (sitting pulse rate and blood pressure) and body temperature	X	X	P, 3h	24h	X	X	X	X	X	X	X	X	X	X	X	X	X	Predose D1 conducted within 2h predose. Postdose assessment 3±1h. Time points may be added at (discretion.

Single 12-lead ECG (supine)	X		P, 3h	24h														X	May be obtained at additional times, if deemed clinically necessary.
Hematology, chemistry, and urinalysis	X	X	P	X	X		X		X		X		X		X	X	X	D1 collected within 2h predose. See Section 10.2.	
AE and concomitant medication recording	X	X	X	X	X	X	X	X	X	X	X	X	X	X	X	X	X	If an AE of an ISR is reported, see Section 8.2.6.2.	
Lebrikizumab PK sample			P	24h	X	X	X	X	X	X	X	X	X	X	X	X	X	D1 collected within 2h predose.	
Immunogenicity sample			P				X		X						X	X	X	D1 collected within 2h predose.	

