7.3. Lost to Follow-up

A participant will be considered lost to follow-up if they repeatedly fail to return for scheduled visits and are unable to be contacted by the study site. Site personnel or designee are expected to make diligent attempts to contact participants who fail to return for a scheduled visit or were otherwise unable to be followed up by the site.

8. Study Assessments and Procedures

Study procedures and their timing are summarized in the SoA in Section 1.3.

The specifications in this protocol for the timings of safety and sample collection are given as targets to be achieved within reasonable limits. Modifications may be made to the time points based upon emerging clinical information. The scheduled time points may be subject to minor alterations; however, the actual time must be correctly recorded in the CRF.

Immediate safety concerns should be discussed with the sponsor immediately upon occurrence or awareness to determine if the participant should continue or discontinue study intervention.

Adherence to the study design requirements, including those specified in the SoA, is essential and required for study conduct.

All screening evaluations must be completed and reviewed to confirm that potential participants meet all eligibility criteria. The investigator will maintain a screening log to record details of all participants screened and to confirm eligibility or record reasons for screening failure, as applicable.

Section 10.2 lists the laboratory tests that will be performed for this study and Section 10.2.1 provides a summary of the maximum number and volume of invasive samples, for all sampling, during the study. See Section 10.1.9 for details about sample retention and custody.

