8.4. Pharmacokinetics

Blood samples will be collected for measurement of serum concentrations of lebrikizumab as specified in the SoA in Section 1.3.

Instructions for the collection and handling of biological samples will be provided by the sponsor. The actual date and 24-hour clock time of each sample will be recorded.

Study intervention concentration information that may unblind the study will not be reported to investigative sites or blinded personnel until the study has been unblinded.

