8.8. Immunogenicity Assessments

Antibodies to lebrikizumab will be evaluated in blood samples collected from all participants according to the SoA in Section 1.3. Antibodies may be further characterized and/or evaluated for their ability to neutralize the activity of lebrikizumab. To interpret the results of immunogenicity, a venous blood sample will be collected at the same time points to determine the serum concentrations of lebrikizumab. All samples for immunogenicity should be taken predose when applicable and possible.

TE ADA are defined in Section 9.3.4.

Immunogenicity will be assessed by **CCI** [REDACTED]

[REDACTED] Antidrug antibody samples will be stored as per local regulation or IRB/IEC requirements. Samples will be immediately destroyed once lebrikizumab is launched or there is no further request on testing the samples from China authority.

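### Does the blood sampling summary in Protocol 10.2.1 need changing because the SoA marks more PK and immunogenicity draws than it counts?

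*Protocol*

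**What the plan says.** Protocol 10.2.1 describes itself with the sentence "This table summarizes the approximate number of venipunctures and blood volumes for all blood sampling, screening, safety laboratories, and bioanalytical assays during the study". Its rows are:

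- screening tests: 1 sample of 18.5 mL
- hematology and chemistry: 11 samples of 5.5 mL
- pharmacokinetics: 13 samples of 3 mL
- immunogenicity: 5 samples of 10 mL

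The total is 168 mL, with 170 mL given for clinical purposes. A footnote allows extra samples for safety, but it is attached only to the first two rows.

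The opening text of Protocol Section 8 says that this section "provides a summary of the maximum number and volume of invasive samples, for all sampling, during the study".

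The sampling instructions are elsewhere. Protocol 8.4 says "Blood samples will be collected for measurement of serum concentrations of lebrikizumab as specified in the SoA in Section 1.3", and Protocol 8.8 says "Antibodies to lebrikizumab will be evaluated in blood samples collected from all participants according to the SoA in Section 1.3". In the SoA itself (Protocol 1.3) the PK row reads "Lebrikizumab PK sample P 24h X X X X X X X X X X X X X". The row labelled "Immunogenicity sample" carries a predose mark and five further marks.

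**The concern.** The summary and the schedule should agree, and they do not: 13 against 15 for PK and 5 against 6 for immunogenicity. The extra draws are scheduled ones, so the footnote on additional safety samples does not cover them. Section 8 calls the table a maximum, and the schedule appears to exceed it.

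Two things could be at stake. First, the table is the protocol's own statement of blood burden for healthy volunteers. The protocol anticipates no therapeutic benefit for them, although it notes that screening may be of use to them. Second, if a site took its draw counts from the table, scheduled samples would be lost. A missing predose immunogenicity sample would remove the baseline against which treatment-emergent antibodies are defined, and missing PK samples would thin the concentration profile behind Cmax and the AUCs.

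**Working it through.** **Inputs.** Volumes per sample and stated counts come from Protocol 10.2.1. Scheduled draws are the marks in the SoA rows of Protocol 1.3.

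**Step 1: reproduce the stated total.** Total = sum of (volume per sample × number of samples).

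18.5 × 1 + 5.5 × 11 + 3 × 13 + 10 × 5 = 18.5 + 60.5 + 39 + 50 = 168 mL.

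This matches the table, so its internal arithmetic is right. Only the counts are in question.

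**Step 2: count the SoA marks.**

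| Row | Marks in the SoA | Count in 10.2.1 |
|---|---|---|
| PK | predose + 24 h + 13 = 15 | 13 |
| Immunogenicity | predose + 5 = 6 | 5 |
| Hematology/chemistry | screening + 11 = 12 | 11 |

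The hematology/chemistry row agrees if the screening draw is part of the 18.5 mL screening line, which is the natural reading.

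**Step 3: recompute with the SoA counts.**

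18.5 + 60.5 + 3 × 15 + 10 × 6 = 18.5 + 60.5 + 45 + 60 = 184 mL.

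Difference: 184 − 168 = 16 mL (6 mL PK, 10 mL immunogenicity), and 16 / 168 = 9.5%. Against the rounded figure it is 184 − 170 = 14 mL. Correcting one row only gives 174 mL (PK) or 178 mL (immunogenicity), so either gap alone already passes 170 mL.

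**Step 4: how firm are the counts?** The SoA header lists 19 day columns ("Day -28 to -2 -1 1 2 5 8 11 15 22 29 36 43 50 57 64 71 85 99 120"), but rows that should be marked throughout, such as adverse event recording, have 17 cells in the text available. Two columns have been lost or merged. If the loss only removed marks, 15 and 6 are minimums. As a scenario, PK on all 17 listed days from Day 1 gives 18.5 + 60.5 + 51 + 60 = 190 mL, which is 22 mL above 168.

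**Step 5: does anything depend on the table?** Protocol 8.4 and 8.8 send the site to the SoA for both sample types. The opening of Protocol Section 8 also places procedures and their timing in the SoA and makes adherence to it a requirement. On the analysis side, SAP 8.5.1 derives PK parameters from actual sampling times and plots mean profiles at nominal times. SAP 8.6.9 compares titers with the participant's baseline. Neither takes a count or a volume from Protocol 10.2.1.

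**The case for a change.** The best case for a correction is that Section 8 promises a maximum and the schedule goes past it, even past the rounded 170 mL. The row entries are exact integers, so calling the table approximate softens the conflict without removing it. Sharing a venipuncture between PK and immunogenicity does not help, because the table budgets their volumes separately. Damage to the SoA text is also a weak defence: the visible fault is missing cells, and the hematology/chemistry row from the same table agrees with the summary, so there is no sign that marks were added.

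Most of this stands. The two counts disagree on the text, no passage explains the gap, and one section's maximum is another's approximation. What does not follow is a consequence. The size rests on a table with lost columns, so no mark can be tied securely to a day and the exact excess is not established. Any cause is a guess. Leaving out the entries written as times (predose, 24 h) would reproduce 13 and 5, but for PK so would counting only the 13 listed days after discharge, and the fit to the readable marks may itself come from the lost columns. Above all, the stakes set out in the concern need someone to schedule draws from the appendix, and the protocol tells the site not to work that way.

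**Conclusion.** The mismatch is a clerical slip in a supporting appendix, and no change to the plan is called for. On the readable marks the summary is 2 PK samples and 1 immunogenicity sample short: 184 mL against 168 mL, that is 16 mL or 9.5%, spread over about 21 weeks. The SoA governs sampling, so the draws taken are the same whichever figure the appendix prints. The predose antibody baseline and the PK profile are protected by the schedule, and no endpoint or analysis in the protocol or SAP reads the table. Restating it would tidy the document without altering what the trial does or concludes.

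This rests on three assumptions: sites follow the SoA as Protocol 8.4 and 8.8 direct; the marks that survive in the SoA text are genuine; and the screening hematology/chemistry draw belongs to the 18.5 mL screening line. If the intact SoA carries more PK marks, the difference grows (22 mL in the 17-draw scenario), but the reasoning is the same because the SoA would still set the draws.
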